5.12 Study Evaluations

5.12.1 Quality of Life Measures

The study will include the following patient-reported Quality of Life Instruments: ASAS and FACIT-F. These instruments have been previously used and validated in clinical research investigations. These instruments must be completed by the patient before other procedures are done at follow-up visits. When the patient has completed the questionnaires, the forms will be collected from the patient and entered into the case report forms (CRFs) by authorized site personnel. Site personnel should review the forms to ensure all questions were answered and that the intended answers were clearly marked before the patient leaves the study site. The site personnel should ask the patient to complete any missed questions and to clarify any unclear answers. If a patient is unable to complete any or all of the questions, the reason must be documented in the source documentation and in the CRF.

5.12.2 Cardiac Assessment

Cardiac assessment includes a 12-lead ECG test. Electrocardiogram testing will be performed on all patients. ECG will be performed during the post-study visit.

5.12.3 Laboratory Assessments

All hematology, blood chemistries, urinalysis, serum/urine pregnancy tests (if applicable) will be performed by the local laboratory at the investigational site.

5.12.4 Handgrip Strength Testing

HGS determination will be performed using a hand-held dynamometer. On each occasion that HGS is measured, the measurement will be made three times for each hand: 3 measurements for the right hand, followed by 3 measurements for the left hand. A rest period of at least 30 seconds will take place between each individual measurement. During measurement of HGS, the participant should be asked to remove any jewelry that would prevent him/her from exerting maximum squeezing force with either hand. Patient is seated on a chair with feet flat on the floor and facing table/desk. Patient holds dynamometer vertically, supported by table/desk, with elbow flexed approx. 90°. Patient will squeeze the dynamometer with the maximum force for up to four seconds, during which time the administrator says "Squeeze as hard as you can!" and, as patient squeezes "harder!...harder!", and "relax."

5.12.5 Body Composition

Weight will be measured using the calibrated scale dedicated for use in this study. This and all other weights will be collected with the patient wearing only a hospital gown or hospital scrubs (and, if desired, underwear). Patients must be barefoot when weighed. All weights will be recorded in kilograms. Values collected using other scales or other procedures (e.g., while wearing heavy clothing) are prohibited for the purpose of this trial.

BIA and DXA will be performed in an effort to gain insight into the practicality of this methodology and to gain insight into the relationship of body weight changes relative to body composition changes. BIA is a noninvasive method of estimating body composition based on the ability of tissues to conduct an electrical current. Based on this principle, lean tissue conducts electricity better than fat; therefore, the body composition analyzer/scale is able to calculate total body water, total body fat and total body lean mass. DXA scan uses a low amount of radiation to determine fat mass and bone mass and calculates fat-free mass (whole body and segmental).

5.12.6 Biomarkers

Serum samples for all biomarker determination (IL-6, TNF- α , CRP, GH, IGF-1, IGFBP-3) will be drawn and processed at the research site lab.

5.12.7 Physician-Reported Instruments

Patients will be evaluated for performance using the Eastern Cooperative Oncology Group (ECOG), and Karnofsky Scales, at each visit (see Appendices II and III).

5.12.8 Indirect Calorimetry

Resting energy expenditure will be measured by indirect calorimetry. Following an overnight fast, patients will rest in a supine position for at least 30 min before undergoing indirect calorimetry using a ventilated hood technique. This method is termed 'indirect' as the method of collection of gas is from a transparent hood placed over the head of the patient. One end of this hood is connected to the indirect calorimeter to measure carbon dioxide and oxygen content in the expired air, and air is drawn in from the other end of the tube, from which a portion is sampled to measure oxygen and carbon dioxide in the inspired air.

Measurements will be performed for at least 30 min. The measurements performed in the last 20 min will be averaged to calculate REE using the Weir equation (40). This method is currently considered one of the 'gold standard' methods to assess energy expenditure. Respiratory quotient (VCO_2 / VO_2 ratio, RQ) will be calculated as a measure of relative utilization of carbohydrates and fat.

5.12.9 Stair Climbing Power

The patients will be instructed to ascend a standard flight of stairs as quickly as possible, using the handrail if necessary. Time will be recorded to the nearest 0.01 second. The power is calculated in watts by dividing the time elapsed into the product of the body weight, the vertical distance, and the acceleration of gravity (9.8 m/sec²).

5.12.10 Laboratory assays

Serum samples for all biomarker determination (IL-6, TNF- α , GH, IGF-1, IGFBP-3) will be drawn and processed at the research site lab.

5.12.11 Test Meal

Food intake will be measured as a secondary outcome by a free-choice test meal and a food diary. After signing an informed consent, trained personnel will instruct patients on the use of the food diary, review food preferences and perform the food intake analysis. Based on this information, patients will be given free access to food items of their like and instructed to eat as much as they want. This procedure will take place at screening after signing informed consent and review of I/E criteria and on day 7 one (1) hour after dosing. The same food items and amounts will be provided at each meal. Food items will be weighed before and after each test meal and total calories as well as the relative proportion of fat, carbohydrates (CHO) and protein will be measured using FoodWorks version 7.01 (TNC, Long Valley NJ, USA). Changes from baseline in Kcal, fat, CHO and protein consumed will be measured and placebo-treated patients will serve as controls.

We will use a food diary detailing intake for 3 consecutive days (including 1 weekend day and 2 weekdays) to assess patients' nutrient intake and eating patterns. This method has been shown to adequately reflect current dietary intake in this population (2). This diary consists of 6 fields to be completed each day, corresponding to 3 main meals (breakfast, lunch, and dinner) and 3 between-meal snacks (morning, afternoon, and evening). Trained personnel will instruct participants on completion of the food record and later review the records with each participant for accuracy and completeness. Each patient will be asked to complete this diary the week before starting treatment and again three days before the Day 7 visit. Analysis will be done using FoodWorks version 7.01 and will focus on energy intake and the percentage of total energy contributions (% of kcal) from fat, carbohydrate, and protein. Mean intake will be expressed per person per day and per kg of body weight. Mean changes from baseline will be compared between patients randomized to Macimorelin vs. placebo.

5.12.12 Imaging

Imaging will be performed with a 3-Tesla Phillips MRI located at the University of Washington. Patients will lay still for ~30 min in the scanner. The only instruction is that they should swallow little squirts of juice (0.8 ml, just enough to taste the juice) several times, while keeping eyes open and being as still as possible. Imaging data will be analyzed separately for fMRI, DTI and DSFC. Correlations between different imaging modalities and between imaging data and behavioral and physiological measures will be used to extract meaningful biological data.

5.12.13 Data Analysis

5.12.13.1 Statistical Analyses

This is a pilot and exploratory study to assess safety and efficacy. The data generated through this trial will be used to power a future, larger clinical trial. All efficacy variables will be summarized descriptively by treatment using N, mean, SEM and standard deviation. Data from placebo-receiving patients from all groups will be pooled together for the purpose of analyses since their treatment will be identical. Analyses will be done as changes from baseline using paired t-test for continuous variables and Fisher's exact test for categorical variables. Also, one-way ANOVA will be used to compare the differences in outcomes between groups. Appropriate transformations will be applied to the outcome changes to improve distribution toward normality. As recommended by the CONSORT guidelines (1), we will develop both completers and intention-to-treat (ITT) models.

We have selected primary endpoints for each specific aim based on the clinical relevance of each outcome and the research questions proposed. Other endpoints will be considered secondary endpoints that will provide supplemental evidence to the conclusions drawn from these primary variables or will explore different areas. Full disclosure and complete description of all endpoints will be included in public presentations of data to avoid bias. Safety, including adverse events, ECGs, vital signs, and laboratory assessments will be summarized descriptively by treatment group.

Analysis of fMRI data will be as follows: We use a general linear model in analyzing and designing our fMRI experiments. To compare data from different patients, the scan data from each patient must be transformed into a standard anatomical framework. We follow the approach of Frackowiak et al (46) which analyzes the brain into small local volumes, or "voxels." The fMRI signal from each voxel is then subjected to the following transformation and analysis steps:

-Analysis Step 1: Spatio-temporal normalization to a standard brain map, and smoothing to improve the signal to noise ratio.

-Analysis Step 2: Statistical analysis to determine the significance of the activity measured at each voxel. We use an established statistical framework (2, 3) in terms of a general linear model, which incorporates and formalizes the independent explanatory variables in our experiment.

Given the variance of each parameter, we can construct a t-statistic as a measure of the significance of differences in the parameters estimated from different experiments, at different voxels, or in different patients. In practice, we construct a t-statistic out of a particular linear combination of the parameters that describes a quantity of interest. To express this mathematically, we define a contrast vector that specifies a linear combination of parameters. Then the t-statistic is the quantity of interest divided by its standard error. When we calculate a t-statistic at each voxel in an imaged brain, measuring the significance of a difference between parameters from different patients or different experimental conditions, the resulting set is called a statistical parametric map. We use such maps to determine areas of significant activation in the brain during presentation of stimuli or performance of the task. DTI analysis will be performed using the TrackVis software.

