Human Subjects Protocol

VA Puget Sound IRB

**Pilot clinical trial of Macimorelin to assess safety and efficacy in patients with Cancer
Cachexia**

MIRB #00954

Funding Agency: VA/SIBCR

Principal Investigator: [name]

02/06/2018

Abstract

Every year, over 1.5 million individuals in the US are diagnosed with cancer. Cachexia, defined as an involuntary weight loss >5%, and anorexia (decreased food intake and appetite) are present in up to 80% of these patients, decreasing functional performance, quality of life (QOL) and survival. However, treatments for this condition are lacking. Feeding behavior is maintained by a network of interconnected brain areas, including the hypothalamus and striatum. The striatum signals the rewarding effects of food, while the hypothalamus responds to states such as hunger and satiety. The extent to which cancer cachexia and anorexia affect these circuits and their response to different interventions have not been characterized. In non-cancer models, administration of ghrelin or its mimetics decreases resting energy expenditure (EE) and inflammation and increases food intake and food reward. This leads to an increase in lean body mass (LBM) and fat mass. However, its role in cancer anorexia-cachexia syndrome (CACS) is not well-characterized. To study the pathways regulating appetite in this setting and the mechanisms mediating the effects of ghrelin mimetics on food intake and reward, we will perform functional Magnetic Resonance Imaging studies on cancer patients with cachexia before and after receiving the ghrelin mimetic macimorelin for 7 days. There are no published reports studying the different components of CACS in the human brain. We will assess its effects on hypothalamic and reward centers in the brain, and the effects of macimorelin on brain activity related to food intake.

Hypothesis: in CACS, compared to placebo, macimorelin will: a) increase appetite, food intake, and food reward, b) decrease REE and inflammation, c) improve QOL.

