3.0 Objectives

3.1 Primary Objective

To evaluate the safety and efficacy of repeated daily oral administration of macimorelin at different doses for 1 week in view of a development for the treatment of cachexia based using the following parameters:

1. Change of body weight (kg) between day 1 and day 7
2. Change of IGF-1 plasma levels between day 1 (prior to dosing) and day 7
3. Change of quality of life score (Anderson Symptom Assessment Scale, FACIT-F) between day 1 and day 7

Hypothesis: One week administration of Macimorelin will be well tolerated and will improve body weight, plasma IGF-1, and quality of life compared to one week administration of placebo in patients with cancer cachexia.

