5.12.13.2 Study Endpoints

Primary efficacy parameters:

- Change of body weight (kg) between day 1 and day 7
- Change of IGF-1 plasma levels between day 1 (prior to dose) and day 7
- Change of quality of life score (Anderson Symptom Assessment Scale, FACIT-F) between day 1 and day 7

Secondary efficacy parameters:

- Food intake as measured by a food diary to be recorded for 3 days before days 1 and 7 and by a test meal administered at screening and on day 7.
- Change of appetite measured by a validated visual analogue scale between day 1 and day 7.
- Body composition as measured by bio-impedance on days 1 and 7.
- Muscle strength as measured by handgrip strength and stair climbing power.
- Energy expenditure as measured by indirect calorimetry.

- Change in GH, IGFBP-3, CRP, IL-6 and TNF- α and glucose between day 1 and day 7.
- Changes in reward from food as measured by brain functional Magnetic Resonance Imaging (fMRI).
- Changes in functional brain connectivity as assessed by Resting State Functional Connectivity (RSFC) imaging and Diffusion Tensor Imaging (DTI).

Safety parameters:

- Clinical laboratory parameters: complete blood count (CBC), comprehensive metabolic panel (CMP), urinalysis (UA)
- Vital signs,
- Electrocardiogram (ECG) changes pre and post-dosing at day 1 and day 7 and on the post-study visit.
- Recording of adverse events from day 1 to day 7

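### Unspecified transformations are to be applied to change scores; for the skewed secondary markers, logging the Day 1 and Day 7 values before differencing is the better rule

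*Combined protocol and SAP*

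**What the plan says.** Section 5.12.13.1, repeated in the Statistics row of the Synopsis, sets out the analysis of continuous outcomes in three statements: "Analyses will be done as changes from baseline using paired t-test for continuous variables and Fisher's exact test for categorical variables"; "one-way ANOVA will be used to compare the differences in outcomes between groups"; and "Appropriate transformations will be applied to the outcome changes to improve distribution toward normality".

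This is the only transformation rule for the clinical and laboratory endpoints. It acts on the change, not on the measurement. It does not name a transformation, the variables concerned, a criterion for choosing, or what to do with zero or negative changes.

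Section 5.12.13.2 defines the laboratory endpoints as differences that can take either sign. The secondary set is "Change in GH, IGFBP-3, CRP, IL-6 and TNF- α and glucose between day 1 and day 7"; the primary marker is "Change of IGF-1 plasma levels between day 1 (prior to dose) and day 7". The expected direction differs by endpoint. The Abstract hypothesis includes "b) decrease REE and inflammation", while Section 3.1 expects that macimorelin "will improve body weight, plasma IGF-1, and quality of life compared to one week administration of placebo".

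**The concern.** Concentrations such as CRP, IL-6, TNF-alpha and GH are commonly right-skewed, with changes that scale with the starting level. The usual remedy is to log each measurement and then subtract. The plan subtracts first and transforms afterwards, and the order matters for two reasons.

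- The transformations most often used for right skew, the log and the square root, do not exist for a negative change. If the hypothesis on inflammation is right, most macimorelin patients will have negative changes in those markers.
- Once the baseline has been subtracted, proportional change cannot be recovered.

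The choice is also left open until about 12 values have been seen, too few to judge normality reliably. At stake are the power and readability of the marker results. So is their use in planning: Section 5.12.13.1 says the data will be used to power a larger trial, and a standard deviation on an unnamed, data-chosen scale is hard to carry into a sample-size formula.

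**Working it through.** The documents give no SD of change, share of negative changes, alpha or power for these endpoints, so there is no figure to reproduce. Group sizes come from the Abstract (6 macimorelin, 2 placebo) and Section 2.1 (placebo pooled, 4 + 2 = 6). Everything else below is an assumption.

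**1. Would a log or root of the changes fail?** Take placebo with mean change zero and macimorelin with mean gain d SDs, changes normal. Then P(at least one negative change) = 1 − 0.5^6 × Φ(d)^6.

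- d = 0: 1 − 0.5^12 = 99.98%.
- d = 2: 1 − 0.0156 × 0.977^6 = 98.6%.

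So even with a strong upward effect, a plain log or root would almost certainly be undefined for someone.

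**2. How many changes are negative?** It depends on the endpoint.

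- Weight, mean gain 0.8 kg, assumed SD 0.8 to 2.0 kg: Φ(−0.8/SD) = 16% to 34%.
- IGF-1, mean rise 50 ng/mL, assumed SD 25 to 100 ng/mL: Φ(−50/SD) = 2% to 31%.
- A log-normal marker that halves: share negative = Φ(ln 2 / (s√(2(1−ρ)))), where s is the log SD and ρ the correlation between days. At s = 1.0, ρ = 0.6 this is Φ(0.693/0.894) = 78%. At s = 0.7, ρ = 0.8 it is Φ(0.693/0.443) = 94%.

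**3. Does a transformation that accepts negative values repair it?** Take two illustrative CRP falls, 100 to 50 and 4 to 2. Both are halvings, but the changes are −50 and −2. A cube root gives −3.7 and −1.3. No one-to-one function of the change can make them equal. The difference of logs gives −0.69 for both.

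**4. What does it cost in power?** Simulated trials, 6 v 6, log-normal marker, two-sample t-test, two-sided 5%. Each cell shows raw change / cube root of change / difference of logs.

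| log SD, correlation | Halving | Doubling |
|---|---|---|
| 0.7, 0.6 | 22 / 30 / 41% | 35 / 40 / 41% |
| 0.7, 0.8 | 37 / 49 / 69% | 55 / 65 / 68% |
| 1.0, 0.6 | 10 / 18 / 23% | 14 / 23 / 23% |
| 1.0, 0.8 | 15 / 28 / 40% | 23 / 37 / 40% |

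Repeat runs agree to within about two percentage points. For a 20% fall, every method has at most 12% power.

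**5. False positives.** With no effect, the raw change rejects in about 3-4% of trials, a pre-chosen cube root in about 5.0-5.6%, and the difference of logs in about 5%. Picking the smallest p-value from three or four sign-tolerant options raises this to about 6-8%.

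**The case against.** The plan never names a log. Cube root, inverse hyperbolic sine, Yeo-Johnson and rank-normal scores all accept negative changes, so the instruction can be followed without dropping patients or adding constants. This stands, and it rules out the reading that the analysis cannot be computed.

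A reader might also infer that about half of all changes will be negative. The documents give no such figure. It fits only a mean change of zero, as might hold on placebo, and the plan's hypotheses point to fewer negatives for weight and IGF-1 and more for inflammation.

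It is tempting, too, to measure the loss against the raw change. But the plan says changes will be transformed, so the cube root is the fairer comparator and the gap is smaller. The gain also depends on direction. For a doubling, the direction of interest for GH under a GH secretagogue, the cube root and the logs differ by at most three percentage points.

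Finally, the stated aim of the transformation is normality, not significance. The named markers are secondary in a study described as pilot and exploratory, with no power target. The weight and IGF-1 efficacy criteria are fixed in original units (Section 5.1). All of this is fair and limits the weight of the point. It does not answer the loss of the baseline, nor the absence of any named scale.

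**Conclusion.** The point holds as a better-method recommendation of modest size. For skewed markers the rule transforms the wrong quantity, and the standard alternative is available at almost no cost. Under the assumptions above, the power given up for a halving is 5 to 20 percentage points against the cube root of the change (18% v 23% up to 49% v 69%) and 13 to 32 points against the raw change. For a doubling it is 0 to 3 points against the cube root. These sizes rest on assumed log-normality, SDs, correlations and effects; none comes from the documents.

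A reader might infer that leaving the choice open lets the result pick the method and so invalidates the tests. The documents do not support that. A fixed choice keeps the error rate near or below 5%, and even deliberate selection of the best of a few options takes it only to about 6-8%. Nor is it certain that markers would be analysed on an unsuitable scale: the text permits that outcome but does not require it.

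**What to change.** In Section 5.12.13.1 and the Synopsis, delete the sentence that transforms outcome changes and replace it with named rules:

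- CRP, IL-6, TNF-alpha and GH: take logs of the Day 1 and Day 7 values, analyse the difference of logs, and report geometric mean ratios with 95% CI.
- GH is sampled before and 1 hour after dosing on both days, so analyse the pre-dose and 1-hour values separately.
- State the value to be used for results below the assay limit.
- Weight and IGF-1: keep on the original scale, to match the 0.8 kg and 50 ng/mL criteria.
- Quality of life scores: leave untransformed.
- A permutation test may be added as a check on the untransformed endpoints, but it is optional.

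The cost is SAP wording and one convention for low assay results. No visit, sample or assay changes. The SD of the log ratio can then be used directly in planning the later trial.

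### The fMRI plan calls brain areas significant from a t-statistic at every voxel, without stating a threshold, a multiplicity correction, a drug-effect contrast or pre-specified regions

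*Combined protocol and SAP*

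**What the plan says.** The fMRI analysis is in section 5.12.13.1, with the same text in the Statistics row of the Synopsis. It divides the brain into voxels ("analyzes the brain into small local volumes"). The first step is "Spatio-temporal normalization to a standard brain map, and smoothing to improve the signal to noise ratio". The second is "Statistical analysis to determine the significance of the activity measured at each voxel", for which the protocol says: "We use an established statistical framework (2, 3) in terms of a general linear model". A contrast vector then yields a t-statistic, and the set of t-statistics over the brain is the statistical parametric map. The route ends with "We use such maps to determine areas of significant activation in the brain during presentation of stimuli or performance of the task".

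The section gives no alpha, cut-off, family-wise, false-discovery or cluster correction, search volume or region of interest. It mentions differences between experiments, voxels, patients or conditions in general terms only. It never writes down the contrast that would measure the effect of macimorelin.

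Elsewhere the protocol does say where it expects the effect. The Abstract describes a feeding network "including the hypothalamus and striatum" and says that effects on hypothalamic and reward centers will be assessed. Section 2.3 identifies the striatum as the reward center. Section 5.12.13.2 lists food reward by fMRI as a secondary efficacy parameter. Section 5.5 provides two scanning sessions per patient, one before treatment and one on Day 7.

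**The concern.** A rule that calls areas significant needs a threshold and a search volume. Without them, the number of false activations is uncontrolled, and the areas reported can be chosen after the map has been seen. Section 5.12.12 widens the choice by adding unspecified correlations between imaging and behavioral or physiological measures.

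Two uses of the result are at stake. The Significance paragraph says the study will establish how far abnormal food reward contributes to the syndrome and will validate fMRI for this purpose. Section 5.12.13.1 says the data will be used to power a larger trial, and effect sizes read from areas selected because their t-statistic was high are biased upward.

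**Working it through.** The plan gives no fMRI threshold, voxel count or power, so there is no figure of its own to reproduce. The check asks what follows under stated assumptions.

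**Inputs.**
- From the documents: a t-statistic at each voxel (5.12.13.1); 6 macimorelin and 2 placebo patients (specific aim); placebo pooled from Group 1 (N=4) and Group 2 (N=2), giving 6 (section 2.1 and 5.12.13.1).
- Assumed: 30,000 to 100,000 in-brain voxels; uncorrected two-sided voxel thresholds of p<0.05 or p<0.001.

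**Expected false voxels for one null contrast** = voxels × alpha. This holds whatever the correlation between voxels.
- p<0.05: 30,000 × 0.05 = 1,500; 100,000 × 0.05 = 5,000.
- p<0.001: 30,000 × 0.001 = 30; 100,000 × 0.001 = 100.
- A small search volume behaves differently: 100 × 0.001 = 0.1.

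**Chance of at least one false positive** = 1 − (1 − alpha)^m for m effective independent tests. For m = 100 to 1,000 it is 0.994 to 1.000 at p<0.05, and 0.095 to 0.632 at p<0.001.

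**Simulation of smooth null maps** (64,000 voxels, assumed smoothing of 2.5 voxels full width at half maximum, 60 maps per setting). The mean number of false voxels was 3,221 (6 v 2) and 3,248 (6 v 6) at p<0.05, against 64,000 × 0.05 = 3,200. At p<0.001 it was 66 and 64, against 64. Every map had at least one false voxel at p<0.001. The pooled placebo group does not change this.

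**Selection bias in effect sizes.** A voxel is declared only if its observed group difference, in SD units, exceeds critical t × √(1/n1 + 1/n2).
- 6 v 2 (6 df; √(1/6 + 1/2) = 0.816): 2.45 × 0.816 = 2.0 SD at p<0.05; 5.96 × 0.816 = 4.9 SD at p<0.001.
- 6 v 6 (10 df; √(1/6 + 1/6) = 0.577): 2.23 × 0.577 = 1.3 SD at p<0.05; 4.59 × 0.577 = 2.6 SD at p<0.001.

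Every selected voxel shows at least that difference, even if the true difference is zero.

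**The two-region alternative.** If the two tests are independent, testing each at 0.05 gives a family-wise error of 1 − 0.95² = 0.0975, and testing each at 0.025 gives 1 − 0.975² = 0.049. By Bonferroni, 0.025 each keeps it at or below 0.05 under any correlation.

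Power for an assumed 2-SD difference, from the noncentral t with noncentrality 2/√(1/n1 + 1/n2):

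| Comparison | df | Noncentrality | Two regions, 0.025 each | Whole brain, 1e-6 per voxel |
|---|---|---|---|---|
| 6 v 2 | 6 | 2.45 | 0.39 | 0.0001 |
| 6 v 6 | 10 | 3.46 | 0.78 | 0.0015 |

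The last column is Bonferroni over 50,000 voxels (0.05/50,000 = 1e-6). It assumes the same standardised difference at a voxel as in a region mean.

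**The case against.** The strongest reply is that silence is not a decision. A reader might infer that the plan prescribes uncorrected whole-brain maps. It does not: it states no threshold either way, and the cited framework may supply one, which cannot be checked from these documents. This stands, so the false-voxel counts are conditional on an uncorrected threshold over the whole brain. The citation still fixes nothing in advance, because the protocol takes no rule from it.

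A reader might also infer that the trial names no brain regions. It does, in the Abstract and section 2.3, and reported areas could be compared with those targets. The gap is that the analysis section does not use them.

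It may also be said that the quoted sentence concerns activation during stimuli or task, not a treatment comparison. That is correct, and it exposes a further gap: the treatment contrast is defined nowhere.

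Finally, the study is labelled pilot and exploratory, fMRI is one of eight secondary items, it does not enter the adequate-efficacy rule in section 5.1, and full disclosure of all endpoints is promised. This lowers the weight of the point. It does not remove it, because the text claims significance, the data are meant to power a later trial, and disclosure does not control false positives.

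**Conclusion.** The point holds in conditional form. The fMRI plan sets out a route from voxel-wise t-statistics to significant areas with no threshold, no correction, no drug-effect contrast and no use of the regions that the aims name. If the maps are thresholded voxel by voxel without correction, 1,500 to 5,000 false voxels at p<0.05, or 30 to 100 at p<0.001, are expected per null contrast. These figures rest on the assumed 30,000 to 100,000 voxels and on a whole-brain search.

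It would go too far to treat the between-arm comparison as having 6 degrees of freedom. That is the 6 v 2 case. The stated pooling gives 6 v 6 and 10, provided the Group 1 placebo patients have comparable scans. The documents do not show this: Group 1 was completed in Houston, and section 5.12.12 places imaging at the University of Washington. Nor do the documents support reading the fMRI endpoint as confirmatory. It is secondary and exploratory, and the plan should be changed on that footing.

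**What to change.** Amend section 5.12.13.1 and the matching Synopsis text as follows.

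- **Key fMRI endpoint.** Pre-specify the change from screening to Day 7 in the mean food-stimulus contrast within two named regions, hypothalamus and striatum, with the region masks fixed before any Day 7 map is seen. Compare macimorelin with placebo, with correction over the two regions, for example 0.025 each.
- **Whole-brain maps.** Report them as exploratory, with a stated family-wise error corrected threshold.
- **Placebo group.** State whether Group 1 placebo patients have comparable scans, and so whether the comparison is 6 v 2 or 6 v 6.
- **Planning the later trial.** Take fMRI effect sizes from the two pre-named regions, not from areas selected on the map.

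The cost is plan wording and standard software options. Fewer voxels will be called significant, and at 6 v 2 power stays low (0.39 for a 2-SD difference), so estimates with confidence intervals should carry the report. The endpoint keeps its secondary, exploratory status.
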